## 6.4 Efficacy

All efficacy assessments should be performed prior to administration of study treatment.

It is important to **perform the IGA before the PASI**, as the knowledge of PASI scoring can potentially influence how the evaluator scores the IGA. Therefore, the following order should be applied when performing the efficacy assessments during study visits:

- Investigator’s Global Assessment (IGA mod 2011; scale from 0 – 4)
- Psoriasis Area and Severity Index (PASI; score from 0 – 72)
- Rebound assessment

### 6.4.1 Investigator’s global assessment (IGA mod 2011)

IGA mod 2011 will be conducted for overall psoriatic disease as indicated in [Table 6-1](#). It is recommended that the same evaluator conducts the assessment throughout the study whenever possible.

The IGA mod 2011 rating scale for overall psoriatic disease is shown in [Table 6-2](#).

The IGA mod 2011 scale has been used in the core studies (e.g., CAIN457A2302 and CAIN457A2303), and in secukinumab phase II studies in collaboration with Health Authorities, in particular the FDA.

The IGA mod 2011 used in this study is static, i.e., it refers exclusively to the subject’s disease state at the time of the assessments, and does not attempt a comparison with any of the subject’s previous disease states, whether at baseline of core study or at a previous visit.

The IGA mod 2011 score will be recorded in the eCRF.

**Table 6-2 The IGA mod 2011 rating scale**

Score	Short description	Detailed description
0	Clear	No signs of psoriasis. Post-inflammatory hyperpigmentation may be present.
1	Almost clear	Normal to pink coloration of lesions; no thickening; no to minimal focal scaling
2	Mild	Pink to light red coloration; just detectable to mild thickening; predominantly fine scaling
3	Moderate	Dull bright red, clearly distinguishable erythema; clearly distinguishable to moderate thickening; moderate scaling
4	Severe	Bright to deep dark red coloration; severe thickening with hard edges; severe / coarse scaling covering almost all or all lesions

Note: Involvement of nails is not part of the assessment.

Based on this scale, a subject will be considered as IGA 0 or 1 responder if the subject achieves a score of 0 or 1 and improved by at least 2 points on the IGA scale compared to baseline.

### 6.4.2 Assessment of psoriasis area and severity index (PASI)

The investigator or qualified designee will complete the PASI assessment as indicated in [Table 6-1](#). Whenever possible, the same evaluator should perform this assessment at all visits.

A PASI score (Fredriksson and Pettersson 1978, Weisman et al 2003, Gottlieb et al 2005) will be derived as indicated in Table 6-3. The head, trunk, upper limbs and lower limbs are assessed separately for erythema, thickening (plaque elevation, induration), and scaling (desquamation). The average degree of severity of each sign in each of the four body regions is assigned a score of 0-4. The area covered by lesions on each body region is estimated as a percentage of the total area of that particular body region. Further practical details help the assessment:

1. The neck is assessed as part of the head.
2. The axillae and groin are assessed as part of the trunk.
3. The buttocks are assessed as part of the lower limbs.
4. When scoring the severity of erythema, scales should not be removed.

**Table 6-3 The PASI scoring system**

Body region	Erythema (E)	Thickening (plaque elevation, induration, I)	Scaling(desquamation) (D)	Area score (based on true area %, A)*
Head (H) †	0=none	0=none	0=none	0 = 0%
	1=slight	1=slight	1=slight	1 = 1-9%
	2=moderate	2=moderate	2=moderate	2 = 10-29%
	3=severe	3=severe	3=severe	3 = 30-49%
	4=very severe	4=very severe	4=very severe	4 = 50-69%
				5 = 70-89%
Trunk (T) ‡	0=none	0=none	0=none	0 = 0%
	1=slight	1=slight	1=slight	1 = 1-9%
	2=moderate	2=moderate	2=moderate	2 = 10-29%
	3=severe	3=severe	3=severe	3 = 30-49%
	4=very severe	4=very severe	4=very severe	4 = 50-69%
				5 = 70-89%
Upper limbs (U)	0=none	0=none	0=none	0 = 0%
	1=slight	1=slight	1=slight	1 = 1-9%
	2=moderate	2=moderate	2=moderate	2 = 10-29%
	3=severe	3=severe	3=severe	3 = 30-49%
	4=very severe	4=very severe	4=very severe	4 = 50-69%
				5 = 70-89%
Lower limbs (L) §	0=none	0=none	0=none	0 = 0%
	1=slight	1=slight	1=slight	1 = 1-9%
	2=moderate	2=moderate	2=moderate	2 = 10-29%
	3=severe	3=severe	3=severe	3 = 30-49%
	4=very severe	4=very severe	4=very severe	4 = 50-69%
				5 = 70-89%
			6 = 90-100%	

\*Percentage (not score) of body region (not whole body) affected will be entered in the eCRF

†Neck is assessed as part of the Head (H) body region.

‡Axillae and groin are assessed as part of the Trunk (T) body region.

§Buttocks are assessed as part of the Lower limbs (L) body region.

Because the head and neck, upper limbs, trunk and lower limbs correspond to approximately 10%, 20%, 30% and 40% of the body surface area, respectively, the PASI score is calculated using the formula:

$$\text{PASI} = 0.1(\text{E}_H + \text{I}_H + \text{D}_H)\text{A}_H + 0.2(\text{E}_U + \text{I}_U + \text{D}_U)\text{A}_U + 0.3(\text{E}_T + \text{I}_T + \text{D}_T)\text{A}_T + 0.4(\text{E}_L + \text{I}_L + \text{D}_L)\text{A}_L$$

The keys for the letters are provided in [Table 6-3](#).

PASI scores can range from a lower value of 0, corresponding to no signs of psoriasis, up to a theoretic maximum of 72.0.

The **investigator** is only responsible for collecting the **components** or scoring signs and total regional area. PASI calculations, including changes over time will be done by Novartis via the PASI Score eCRF. At Week 52, the investigator or qualified designee should ensure that all the information required for the PASI calculation was entered into the PASI Score eCRF at Week 52 and that a PASI score is available prior to contacting IRT. The Investigator or qualified designee will enter the Week 52 PASI score into the IRT system at Week 52 before subject receives the study treatment.

Based on PASI at Week 52, a subject to be eligible must be either a PASI 75 responder or partial responder according to the definitions stated below:

- PASI 75 responders: subjects with PASI 75 response (subjects achieving  $\geq 75\%$  improvement [reduction] in PASI score compared to baseline of the core study) at Week 52
- Partial responders: subjects with PASI 50 response (subjects achieving  $\geq 50\%$  improvement [reduction] in PASI score compared to baseline of the core study, but not achieving a PASI 75 response) at Week 52

During the study, at each visit, the PASI score will be calculated and response will be classified according to the definitions from CHMP guidelines for psoriasis [CHMP/EWP/2454/ 02 2004](#)

- **PASI 75 response:** subjects achieving  $\geq 75\%$  improvement (reduction) in PASI score compared to baseline of the core study are defined as PASI 75 responders
- **PASI 50 response:** subjects achieving  $\geq 50\%$  improvement (reduction) in PASI score compared to baseline of the core study are defined as PASI 50 responders
- **PASI 90 response:** subjects achieving  $\geq 90\%$  improvement (reduction) in PASI score compared to baseline of the core study are defined as PASI 90 responders
- **PASI 100 response/remission:** complete clearing of psoriasis (PASI=0)
- **Relapse:** when the achieved maximal PASI improvement from baseline of core study is reduced by  $>50\%$

For subjects in PASI 75 responder group and entering the randomized withdrawal period, PASI response status at each visit (after Week 52 visit) will be calculated to determine if subject will enter the treatment period. PASI at the visit will be compared to the PASI baseline of the core study to assess if subject meets criteria for "**first full relapse**" (loss of  $>50\%$  of maximum PASI gain compared to PASI baseline of the core study). Sites will have to enter relapse assessment into eCRFs and update the IRT at each visit in randomized withdrawal period. Subjects with first full relapse then stop randomized withdrawal period and enter treatment period.

### 6.4.3 Assessment of rebound

Rebound of disease will be assessed as indicated in [Table 6-1](#).

In addition to the assessment of PASI, the investigator will assess whether new pustular psoriasis, or new erythrodermic psoriasis, or more inflammatory psoriasis occurred (yes/no).

### Definitions related to rebound

- **Rebound:** A Subject experiences a rebound, if PASI increases to > 125% of baseline (where baseline is the PASI at the randomization of the core study) PASI, or if new pustular psoriasis, or new erythrodermic psoriasis, or more inflammatory psoriasis occurs within 8 weeks after the last dose of study treatment has been administered.

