## Glossary of terms

Term	Definition
Assessment	A procedure used to generate data required by the study
Control treatment	Drugs(s) used as a comparator to reduce assessment bias, preserve blinding of investigational drug, assess internal study validity, and/or evaluate comparative effects of the investigational drug.
Core studies	Refers to the secukinumab phase III studies (e.g., CAIN457A2302 or CAIN457A2303 and other secukinumab phase III studies) from which subjects meeting the inclusion/exclusion criteria will potentially enter the extension study CAIN457A2302E1
Enrollment	Point/time of subject entry into the study; the point at which informed consent must be obtained (i.e. prior to starting any of the procedures described in the protocol).
Epoch	The planned stage of the subjects' participation in the study. Each epoch serves a purpose in the study as a whole. Typical epochs are: determination of subject eligibility, wash-out of previous treatments, exposure of subject to treatment or to follow-up on subjects after treatment has ended.
Investigational treatment	The drug whose properties are being tested in the study; this definition is consistent with US CFR 21 Section 312.3 and is synonymous with "investigational new drug" or "investigational medicinal product."
Medication number	A unique identifier on the label of each investigational/study drug package in studies that dispense medication using an IRT system
Period	A minor subdivision of the study timeline; divides phases into smaller functional segments such as screening, baseline, titration, washout, etc.
Premature subject withdrawal	Point/time when the subject exits from the study prior to the planned completion of all study treatment administration and assessments; at this time all study treatment administration is discontinued and no further assessments are planned
Randomization number	A unique identifier assigned to each randomized subject, corresponding to a specific treatment arm assignment
Stop study participation	Point/time at which the subject came in for a final evaluation visit or when study treatment was discontinued whichever is later
Study treatment	Any treatment administered to the subject as part of the required study procedures; includes investigational treatment and any control treatments

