- To assess the efficacy of secukinumab 150 mg or 300 mg in subjects with moderate to severe chronic plaque-type psoriasis with respect to DLQI 0 or 1 achievement, compared to placebo over time in subjects who were PASI 75 responders at Week 52, over time for subjects who were re-treated after relapse with secukinumab 150 mg or 300 mg, and over time in subjects who were partial responders at Week 52.
- To assess the efficacy of secukinumab 150 mg or 300 mg in subjects with moderate to severe chronic plaque-type psoriasis with respect to EuroQOL 5-Dimension® Health Questionnaire (EQ-5D®) score, compared to placebo over time in subjects who were PASI 75 responders at Week 52, over time for subjects who were re-treated after relapse with secukinumab 150 mg or 300 mg, and over time in subjects who were partial responders at Week 52.
- To investigate the effects of treatment with secukinumab 150 mg or 300 mg on the occurrence of rebound following cessation of therapy, in subjects who were PASI 75 responders at Week 52, for subjects who were re-treated after relapse with secukinumab 150 mg or 300 mg, and in subjects who were partial responders at Week 52.
- To assess the efficacy of secukinumab 150 mg or 300 mg in subjects with moderate to severe chronic plaque-type psoriasis with respect to relapse, compared to placebo **in subjects who were PASI 75 responders at Week 52.**
- To investigate the development of immunogenicity (IG) against secukinumab over time.

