- c. Secukinumab 300 mg PFS group: Two s.c. injections of secukinumab 150 mg in PFS at randomization (Week 52) and thereafter every 4 weeks up to Week 152 (or until first full relapse).
- d. Placebo secukinumab 300 mg PFS: Two s.c. injections of placebo secukinumab 150 mg in PFS at randomization (Week 52) and thereafter every 4 weeks up to Week 152 (or until first full relapse).

Subjects in the randomized withdrawal period experiencing a **first full relapse** (a loss of >50% of the maximum PASI gain compared to baseline of the core study) at any scheduled visit after Week 52 during the randomized withdrawal period, will enter the **treatment period**. The dose regimen in treatment period (**loading dose and treatment thereafter**) is described in [Table 3-1](#).

**Table 3-1 Loading dose regimen at time of first full relapse\* and treatment thereafter (treatment period) between Week 52 and Week 156**

Groups at time of randomization (Week 52)	Treatment period Loading dose regimen at time of first full relapse* and treatment thereafter
Secukinumab 150 mg PFS	Two s.c. injections of placebo secukinumab 150 mg in PFS once weekly for three weeks (1 week, 2 weeks and 3 weeks later). After 4 weeks following relapse the routine dosing with secukinumab 150 mg regimen every 4 weeks dosing is continued thereafter.
Placebo secukinumab 150 mg PFS	One s.c. injection of secukinumab 150 mg in PFS plus one s.c. injection of placebo secukinumab 150 mg in PFS once weekly for four weeks (at the visit where the relapse was diagnosed, 1 week, 2 weeks and 3 weeks later). After 4 weeks following relapse the routine dosing with secukinumab 150 mg regimen every 4 weeks dosing is continued thereafter.
Secukinumab 300 mg PFS	Two s.c. injections of placebo secukinumab 150 mg in PFS once weekly for three weeks (1 week, 2 weeks and 3 weeks later). After 4 weeks following relapse the routine dosing with secukinumab 300 mg regimen every 4 weeks dosing is continued thereafter.
Placebo secukinumab 300 mg PFS	Two s.c. injection of secukinumab 150 mg in PFS plus once weekly for four weeks (at the visit where the relapse was diagnosed, 1 week, 2 weeks and 3 weeks later). After 4 weeks following relapse the routine dosing with secukinumab 300 mg regimen every 4 weeks dosing is continued thereafter.

\*first full relapse: (a loss of >50% of the maximum PASI gain compared to baseline of the core study)

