### **3.3 Rationale of dose/regimen, duration of treatment**

The doses and regimens selected for secukinumab are projected to deliver high efficacy while at the same time ensuring subject safety. The proposal to continue treatment with s.c. doses of 150 mg and 300 mg administered every four weeks, as well as the additional treatment duration of 208 weeks (leading to an overall treatment period [core plus extension] of 260 weeks) is based on the need for efficacy and safety information during chronic treatment in subjects suffering from chronic plaque-type psoriasis.

The rationale of the dose/regimen for re-treatment after full relapse is supported by model-based considerations. These model-based predictions are subject to caveats and assumptions, but appear to provide plausible guidance. The predictions are considered as extrapolations, as they are made for regimens, time points, subject subsets and withdrawal/re-treatment patterns for which limited or no data is available, as they have not (or not in exactly this way) been studied so far (which is the nature of the current status of development of secukinumab in psoriasis).

The inclusion of a randomized withdrawal treatment period will allow assessing time to relapse and frequency of rebound after cessation of treatment, compared to continuous treatment. This is in line with guidelines for the development of drugs to treat psoriasis ([CHMP/EWP/2454/02](#)).

[figure not shown]
The switch from the lyophilisate to the more convenient prefilled syringe is supported by the results of clinical study CAIN457A2106, which has shown that the exposure profiles of both formulations are virtually identical. This will also remove the need to have unblinded pharmacists involved in the study; these were necessary in the core studies to ensure the double-blind.

Model-based predictions in [Figure 3-2](#) suggest:

- Subjects lose PASI 75 response after withdrawal at an approximate rate of 10% per month (see [Figure 3-2](#) left).

- Substantially less subjects show a full relapse, the predictions reaching 10% after four months (see [Figure 3-2](#) right).

[figure not shown]
**Figure 3-2 Model-based prediction of % PASI 75 responders and % of subjects relapsing during a period of 6 months after either continuous treatment or of withdrawal (based on responders at Week 52)**

Model base exploration with high and unquantifiable uncertainty, thus no intervals are provided

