### **Rebound**

Rebound is defined as a worsening of PASI of > 125% of the value at baseline (core study), or new pustular, erythrodermic or more inflammatory psoriasis occurring within 8 weeks of stopping therapy (i.e., if this definition is fulfilled at more than 8 weeks after last study treatment administration, this is not defined as rebound). The number and percentage of subjects experiencing rebound will be presented by visit and treatment group.

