#### Table 1-2 The PASI scoring system

\* Percentage (not score) of body region (not whole body) affected will be entered in the eCRF

+ Neck is assessed as part of the Head (H) body region.

‡ Axillae and groin are assessed as part of the Trunk (T) body region.

§ Buttocks are assessed as part of the Lower limbs (L) body region.

The following definitions are possible efficacy evaluations that can be used in clinical trials in psoriasis (CHMP/EWP/2454/02, 2004):

- **PASI non response:** subjects achieving <50% improvement (reduction) in PASI score compared to baseline are defined as PASI non responders
- **Partial response**: subjects achieving ≥ 50% improvement (reduction) in PASI score but less than 75% compared to baseline are defined as partial responders
- **PASI 50 response**: subjects achieving ≥ 50% improvement (reduction) in PASI score compared to baseline are defined as PASI 50 responders
- **PASI 75 response**: subjects achieving ≥ 75% improvement (reduction) in PASI score compared to baseline are defined as PASI 75 responders

Novartis	Confidential	Page 32
RAP Module 3	9-Apr-2018 (1:15)	Secukinumab / AIN457A2302E1

- **PASI 90 response**: subjects achieving ≥ 90% improvement (reduction) in PASI score compared to baseline are defined as PASI 90 responders
- **PASI 100 response**: complete clearing of psoriasis (PASI=0)
- **Relapse**: when the achieved maximal PASI improvement from baseline PASI in core is reduced by >50%
- **Rebound-like event**: defined as increase of PASI of more than 25% from baseline value or occurrence of new pustular, new erythrodermic or more inflammatory psoriasis **after** stopping therapy
- Rebound: defined as rebound like event occurring within 8 weeks of stopping therapy

The analysis of rebound will be done for the follow-up period.

The number and percentage of subjects experiencing rebound and rebound like events will be presented by treatment group as follows:

- For rebound, all assessments done up to 8 weeks will be summarized.
- Similarly for rebound like events, all assessments done up to 12weeks will be summarized.
  - 1. Rebound up to 8 weeks: For this time-point the worst outcome (i.e. rebound like event=yes) prior to this cut-off is considered (e.g. if a subject had >25% PASI increase at Week 260, but not at Week 264 the subject would be considered as rebounder for this "up to 8 week timepoint").

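### The rebound window starts at the last study treatment, which includes placebo, and the SAP analyses rebound in follow-up only, so the final analysis omits rebound after randomised withdrawal of secukinumab compared with continued treatment.

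*Protocol*

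**What the plan says.** **Definition.** The Protocol (6.4.3) counts an event as rebound if it occurs "within 8 weeks after the last dose of study treatment has been administered". Section 9.5.1 uses the same clock and adds that "if this definition is fulfilled at more than 8 weeks after last study treatment administration, this is not defined as rebound". The Protocol glossary defines study treatment as "Any treatment administered to the subject as part of the required study procedures; includes investigational treatment and any control treatments".

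**Placebo dosing.** Protocol section 3.1 gives each placebo arm "Two s.c. injections of placebo secukinumab 150 mg in PFS at randomization (Week 52) and thereafter every 4 weeks up to Week 152". A first full relapse ends this regimen sooner.

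**Purpose.** A secondary objective (Protocol 2.2) is to investigate the effects of treatment "on the occurrence of rebound following cessation of therapy, in subjects who were PASI 75 responders at Week 52", and likewise in re-treated subjects and partial responders. Section 3.3 says the withdrawal period will "allow assessing time to relapse and frequency of rebound after cessation of treatment, compared to continuous treatment". The synopsis and section 1.2 also name rebound frequency after stopping secukinumab as something this period will deliver.

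**Collection and protocol analysis.** Footnote 12 of Protocol Table 6-1 requires rebound assessments in both the withdrawal and treatment periods. Section 9.5.1 plans counts by visit and treatment group for Week 52 PASI 75 responders, and section 9 lists both placebo arms among their groups.

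**SAP.** Section 1.9.1.1 states: "The analysis of rebound will be done for the follow-up period". Table 1-4 and section 1.9.6 agree. Rebound is not among the withdrawal-period re-runs in section 1.1. The list of changes from the protocol (1.1.1) announces a new rebound-like event but not the restriction to follow-up. Section 1.9.5 still lists rebound as a secondary variable for all three populations.

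**The concern.** Rebound is a question about what happens when the active drug is taken away. A clock that restarts at each placebo injection, or starts at the final one, does not measure time since secukinumab. An event in a placebo subject can then be labelled rebound, or excluded from it, for reasons unrelated to withdrawal of the drug.

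The withdrawal period is also the only part of the trial with a concurrent randomised group still on secukinumab. If rebound is summarised only in follow-up, the comparison that section 3.3 describes does not appear in the final analysis, and a reader of the SAP's list of changes would not learn that it had gone.

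**Working it through.** **1. The documents' follow-up timing reproduces.** With the last open-label dose at Week 256:
- Week 260: 260 − 256 = 4 weeks (672 h)
- Week 264: 264 − 256 = 8 weeks
- Week 268: 268 − 256 = 12 weeks (2016 h)

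These match Protocol section 3.1 and Appendix 2. For subjects whose last dose was secukinumab, the clock works as intended.

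**2. The clock for placebo subjects in the withdrawal period.** Scheduled visits from Week 56 to Week 156 number (156 − 56)/4 + 1 = 26. Injections are 28 days apart. With ±5-day windows at each end the gap is at most 28 + 5 + 5 = 38 days, which is less than 56. The core study's last secukinumab dose is not stated. I assume Week 48 to Week 52; Week 52 is an outer limit, because the injection at that visit is the first extension dose.

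| Meaning given to the anchor | Consequence for a placebo subject |
|---|---|
| Most recent study treatment | An on-schedule subject is never 8 weeks past it, so the limit excludes no scheduled withdrawal visit |
| Final study treatment in the trial | The window opens after the last placebo dose or, for subjects later re-treated, after the last secukinumab dose; in neither case at the original withdrawal |
| Last secukinumab before withdrawal | 48 + 8 = Week 56 to 52 + 8 = Week 60, so 1 visit (Week 56) or 2 visits (Weeks 56 and 60) |

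Only the third reading measures rebound after withdrawing secukinumab, and the protocol's wording does not give it.

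**3. Whether the SAP resolves it.** Section 1.9.1.1 refers to stopping therapy without saying whether therapy means secukinumab. The footnote to Table 1-5 anchors the 8- and 12-week time-points to the last study drug administration. For relapse in follow-up, the table in section 1.9.7 sets time zero at the last active treatment or the last placebo administration, so a placebo anchor is a realistic reading.

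**4. Example.** A placebo subject without relapse is dosed through Week 152, leaves at Week 156 and is followed at Weeks 160 and 164. Time since placebo is 4, 8 and 12 weeks. Time since secukinumab runs from 156 − 52 = 104 to 164 − 48 = 116 weeks.

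**5. What the 26 visits do not mean.** Let B be the core baseline PASI. A PASI 75 responder has gained at least 0.75B, so at a maximum gain of exactly 0.75B full relapse means the gain has fallen below 0.375B. At a PASI above 1.25B the gain is below B − 1.25B = −0.25B. Rebound by the PASI criterion is therefore already a full relapse, and relapse at a scheduled visit ends the withdrawal period. At scheduled visits a subject can have at most one such event in that period, at the relapse visit. Only the pustular, erythrodermic and more-inflammatory criteria escape this limit.

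**The case against.** The strongest reply has four parts.

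- **Rebound is measured.** It is collected in the withdrawal period, and the protocol plans to tabulate it by arm. This stands. A reader might infer that the objective goes unmeasured; the documents do not support that. The gap is in what this SAP analyses.
- **This SAP mainly covers the final analysis.** Section 1.1 says so and refers to analyses already conducted. A withdrawal-period rebound table may exist under a plan that is not among these documents, so one cannot conclude that the arms were never analysed. But the Week 68 analysis (Protocol 9.6) covers data only to Week 68, while withdrawal runs to Week 156, and any table using the protocol definition inherits the same anchor.
- **The clock is right for most of follow-up.** Everyone who enters open label receives secukinumab. The rebound objective, unlike the relapse objective, does not ask for a comparison with placebo. Both statements are correct. Even so, section 3.3 does promise the comparison with continuous treatment, and follow-up has no randomised control.
- **Rebound-like events were added for events beyond 8 weeks.** This helps only in part. Section 1.1.1 describes them as occurring at any time after stopping, but section 1.9.1.1 summarises them only to 12 weeks, and the rebound analysis is confined to follow-up.

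It is also tempting to read 26 visits, or the 2 × 138 = 276 planned placebo subjects, as the size of the error. Neither is: the first is a calendar count limited by step 5 of the working, the second a planning denominator. The documents do not say how many classifications would change.

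**Conclusion.** The point holds for the anchor and for the scope of the SAP. As written, the window for placebo subjects does not begin when secukinumab is withdrawn, and the SAP does not repair this. The final analysis contains no rebound summary by randomised arm for the withdrawal period, although the protocol planned one and the data exist; the SAP's list of changes does not disclose the restriction.

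The size is bounded in timing only: with an active-drug anchor, the 8-week window covers 1 to 2 of the 26 scheduled visits, assuming a last core dose at Week 48 to 52. Follow-up results remain valid, though uncontrolled, for subjects whose last dose was secukinumab. A secondary objective is affected. Rebound lies outside the testing strategy, so no confirmatory conclusion changes.

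**What to change.** In the SAP:

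1. Start the rebound window at the last secukinumab dose. For placebo subjects in the withdrawal period this is the last core-study dose; state its week.
2. Add one descriptive table for the withdrawal period by randomised arm, giving rebound (up to 8 weeks) and rebound-like events (any later time before re-treatment). Alternatively, cite an earlier report that used this anchor and covers the period to Week 156.
3. In follow-up, show subjects whose last dose was placebo separately.
4. Reconcile the open-ended description of rebound-like events in section 1.1.1 with the 12-week limit in section 1.9.1.1, and section 1.9.5 with Table 1-4. If the restriction to follow-up is kept for any output, list it in section 1.1.1.

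The cost is wording and one extra descriptive table from PASI and rebound data already collected. No new assessments are needed.
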